9.4 Modified Mini-Mental State Examination (3MS)

9.4.1 3MS Assessment

The 3MS is an examination designed for the assessment of dementia in adults.

The 3MS will be completed at Screening, Check-in on Day -1, and at approximately 24 h after dosing on Day 1. The 3MS will also be completed prior to dosing and at approximately 24 h after dosing on Days 7 and 14.

Baseline will be considered to be on Day -1.

Table 6: 3MS Details

Scale	Number of Items	Score Range Per Item	Total Possible Score	Scoring Interpretation	Data Collection
Modified Mini-Mental State (3MS)	15 items with subscores	Variable Likert scoring for each item	100	Better performance correlated with increasing score. Scores \leq 77 may be indicative of dementia Normal cognition = 78–100 Moderate cognitive impairment \leq 77 Severe cognitive impairment \leq 49	
 Score for each item (0-7) Total score/100

Scoring calculation:

1. When and where born?

1a. Date	Day	(0 or 1)
	Month	(0 or 1)

Year	(0 or 1)
1a. Score = 0 to 3	
1b. Place Town	(0 or 1)
Province/Country	(0 or 1)
1b. Score = 0 to 2	
1 Score = Sum of 1a + 1b (ie, 0 to 5)	
2. Three Words (Number of presentations ____)	
2a. Shoes	(0 or 1)
2b. Blue	(0 or 1)
2c. Modesty	(0 or 1)
2 Score = Sum of 2a + 2b + 2c (ie, 0 to 3)	
3. 3a. Counting Forwards	(0 or 1)
3b. Counting Backwards	(0 to 2)
3c. Spell "World"	(0 or 1)
3 Score = Sum of 3a + 3b + 3c (ie, 0 to 5)	
4. First Recall	
4a. Shoes	(0 or 3)
4b. Blue	(0 or 3)
4c. Modesty	(0 or 3)
4 Score = Sum of 4a + 4b + 4c (ie, 0 to 9)	
5. Today's Date	
5a. Today's date	(0 or 3)
5b. Year	(0 or 3)
5c. Season	(0 or 3)
5d. Month	(0 or 3)
5e. Day of week	(0 or 3)
5 Score = Sum of 5a + 5b + 5c + 5d + 5e (ie, 0 to 15)	

6. Spatial Orientation

- 6a. Province (0 or 1)
- 6b. Country (0 or 1)
- 6c. City (0 or 1)
- 6d. Place (0 or 1)

6e. Street (0 or 1)

6 Score = Sum of 6a + 6b + 6c + 6d + 6e (ie, 0 to 5)

7. Naming

7a. (0 or 1)
 7b. (0 or 1)
 7c. (0 or 1)
 7d. (0 or 1)
7e. (0 or 1)

7 Score = Sum of 7a + 7b + 7c + 7d + 7e (ie, 0 to 5)

8. Four legged animals Score 0 to 10

9. Similarities

9a. (0 to 2)
 9b. (0 to 2)
9c. (0 to 2)

9 Score = Sum of 9a + 9b + 9c (ie, 0 to 6)

10. Repetition

10a. Province (0 to 2)
 10b. Country (0 or 1)
 10c. City (0 or 1)
10d. Place (0 or 1)

10 Score = Sum of 10a + 10b + 10c + 10d (ie, 0 to 5)

11. Obeys commands Score 0 to 3

12. Writing Score 0 to 5

13. Copy

13a. (0 to 4)
 13b. (0 to 4)
13c. (0 to 2)

13 Score = Sum of 13a + 13b + 13c (ie, 0 to 10)

14. 3-Stage command

14a. (0 or 1)
 14b. (0 or 1)
14c. (0 or 1)

14 Score = Sum of 14a + 14b + 14c (ie, 0 to 3)

15. Second Recall

15a.	Shoes	(0 or 3)
15b.	Blue	(0 or 3)
15c.	Modesty	(0 or 3)

15 Score = Sum of 15a + 15b + 15c (ie, 0 to 9)

Total 3MS Score = Sum of Scores for Items 1 to 15 = 0-100

9.4.2 3MS Visit Windows

The acceptable window for 3MS will be within 3 hours prior to next dose for the 24 hours time point. All the 24 hours postdose assessments are intended to be completed prior to next day dosing as applicable.

PD procedures should be carried out in the following order when required: (1) 3MS, (2) CADSS, (3) BPRS, (4) C-SSRS.

9.4.3 3MS Endpoints

Derived endpoints will include:

- 3MS_TS_{CFB} = Total Score Change from Baseline (CFB) = CADSS_TS at each postdose time point – 3MS_TS_B at baseline
- 3MS_TS%_{CFB} = Total Score Percent Change from Baseline (CFB)

9.4.4 3MS Analysis

Tables and listings will be presented for absolute values and derived endpoints described below. Inferential analysis will be provided for the derived endpoints (refer to SAP Section 9.6 for more detailed information).

9.5 Alertness Visual Analogue Scale (VAS)

9.5.1 Alertness VAS Assessment

The VAS alertness scale is designed to assess the alertness of subjects across a continuum scale with values from 0 to 10.

The VAS should be completed prior to TMP-301 administration at Screening, and at approximately 4, 6 and 12 h after dosing on Days 1, 7, and 14. This assessment will also occur on Day 18 prior to Discharge.

9.5.2 Alertness VAS Endpoints

Derived endpoints will include:

- E_{max}(Maximum postdose effect)
- E_{min}(Minimum postdose effect)
- TE_{max}(Time of postdose maximum effect)
- TE_{min}(Time of postdose minimum effect)

E_{max} and E_{min} will be calculated based on the postdose values; the predose value will be excluded.

TE_{max} and TE_{min} will be calculated as the time from time 0 to E_{max} and E_{min} , respectively, as appropriate. The first time of peak effect is used if the value is reported at more than one time point.

9.5.3 Alertness VAS Analysis

Alertness VAS values will be summarized and listed for absolute values and derived endpoints. No inferential analyses will be performed.

9.6 Psychiatric Assessments Analysis

Psychiatric measures at each time point will be summarized by treatment (placebo and each dose of TMP-301) using descriptive statistics and presented graphically. Derived endpoints will also be summarized by treatment using descriptive statistics. Only summary statistics will be output for E_{max} TE_{max} , E_{min} and TE_{min} . Descriptive statistics will include n, mean, standard error (SE), minimum, first quartile (Q1), median, third quartile (Q3) and maximum for all psychiatric assessment values, and endpoints other than TE_{max} and TE_{min} . For TE_{max} and TE_{min} , minimum, Q1, median, Q3 and maximum will be output.

A mixed-effects model for a parallel study design will be used to compare the derived endpoints between treatments (e.g., BPRS_TS_{CFB}, BPRS_TS%_{CFB}, CADSS_TS_{CFB}, CADSS_TS%_{CFB}, 3MS_TS_{CFB}, and 3MS_TS%_{CFB}). The model will include treatment (dosing group), day, and dose (1st or 2nd) as fixed effects, and the baseline measurement as a covariate. P-values for key components of variance, least-square means (LSMeans), and 95% CI for contrasts will be output. For each endpoint, the following comparisons will be made:

- Contrast 1: TMP-301 50 mg BID vs. Pooled Placebo
- Contrast 2: TMP-301 50 mg QD vs. TMP-301 50 mg BID
- Contrast 3: TMP-301 50 mg QD vs. Pooled Placebo
- Contrast 4: TMP-301 XX mg vs. TMP-301 50 mg BID
- Contrast 5: TMP-301 XX mg vs. TMP-301 50 mg QD
- Contrast 6: TMP-301 XX mg vs. Pooled Placebo

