APPENDIX 14. PSYCHIATRIC EMERGENCY MANAGEMENT

Inhibitors or antagonists of mGlu5, including TMP-301, are associated with psychiatric adverse events which can include dissociation and hallucination. Although most psychiatric AEs with this class of drugs are mild, there is a risk of psychiatric AEs evolving into emergencies, where there is an immediate risk of harm to either the treated subject, or others in the subject's surroundings. The purpose of this appendix is to define the procedures for identification and management of potential psychiatric emergencies in subjects enrolled in this study. These procedures have been designed to ensure the safety of subjects and staff and to provide continuity of care through the resolution of the psychiatric emergency.

[Figure 2](#) shows an overview of psychiatric emergency management in this study. The subsequent sections of this appendix provide details of the specific steps in the emergency management procedure. The Investigator(s) implementing this management plan will have 24/7 access to a psychiatrist to assist in the decisions required to implement the plan. Full supporting operational details are described in the psychiatric event monitoring plan (PEMP).

Figure 1: Psychiatric Emergency Management

Psychiatric Adverse Event Monitoring:

Psychiatric AE monitoring follows the same general process of monitoring for any AE as described in Section 7.4 of the protocol. Specifically, subjects will be monitored for evidence of psychiatric AEs from the time of ICF signature to the end of the study in the following ways:

- Study staff observations
 - Open-ended health status questions at the start and end of domiciling periods and observation of subject behavior during domiciling periods
 - Review of subject responses to scheduled BPRS (6.1.8), CADSS (6.1.9), C-SSRS (6.1.10), 3MS (6.1.11) and VAS (6.1.12) assessments
- Spontaneous subject reports of new symptoms or other complaints

If any of these sources raise the suspicion of a psychiatric AE, a formal evaluation by the Investigator will occur to confirm the AE. Once an event is confirmed to be a psychiatric AE, it will be assigned severity (see Section 7.2) and causality (see Section 7.3).

Psychiatric Emergency Determination:

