9.1 Brief Psychiatric Rating Scale (BPRS)

9.1.1 BPRS Assessment

The BPRS scale is designed for the assessment of psychiatric symptoms or disorders (e.g., depression, anxiety, hallucinations, and unusual behavior).

The BPRS should be completed at Screening, Check-in on Day -2, 7 and 14. It will also be completed at approximately 6 and 24 h after dosing on Days 1, 7, and 14.

Baseline will be considered to be on Day -1.

Table 5: BPRS Details

Scale	Number of Items	Score Range Per Item	Total Possible Score	Scoring Interpretation	Data Collection
Brief Psychiatric Rating Scale (BPRS)	18 Items	1-7 point Likert scale 1=not present 2=very mild 3=mild 4=moderate 5=moderately severe 6=severe 7=extremely severe	126	Severity increases with increasing score A score of 18 is generally expected for healthy volunteers. Scores ≥ 25 reflect the presence of psychiatric symptoms and should be considered exclusionary Total Score cutoff criteria for patients diagnosed with schizophrenia or experiencing psychosis are: Mildly ill ≥ 31 Moderately ill ≥ 41 Markedly ill ≥ 53 In- or out patients with paranoid, disorganized or undifferentiated schizophrenia (DSM-IV), BPRS total score ≥ 36 , BPRS psychotic subscore ≥ 23 and at least two BPRS psychosis items $\geq 4^1$	Score for each item (1-7) Score Range: 18-126 Cutoff Score: ≥ 25 If an item is not assessed, the BPRS Total Score will not be computed

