9.2 Clinician Administered Dissociative States Scale (CADSS)

9.2.1 CADSS Assessment

The CADSS scale is designed for the assessment of dissociative states in adults.

The CADSS will be completed at Screening, Check-in on Day -2, and at approximately 6 and 24 h after dosing on Day 1. The CADSS will also be completed prior to dosing and at approximately 6 and 24 h after dosing on Days 7 and 14.

Baseline will be considered to be on Day -1.

Table 5: CADSS Details

Scale	Number of Items	Score Range Per Item	Total Possible Score	Scoring Interpretation	Data Collection
Clinician Administered Dissociative States Scale (CADSS)	23	0-4 point Likert scale 0=not at all 1=mild 2=moderate 3=severe 4=extreme	92	Severity increases with increasing score No official cut off criteria for scoring Baseline scores for normal healthy males were 1.67 (2.96) ²	
 • Score for each item (0-4) Score Range: 0-92 (general dissociation) ○ Of note Items can be segregated into factors e.g. Altered visual and auditory perception (items 2, 9, 10, 11, 16, 18) ○ Altered time and perception (Items 1, 12, 15) Depersonalization (Items 3, 4, 5, 6, 20)³

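### The BPRS and CADSS mean-change contrasts are insensitive to a strong reaction in one subject, and no postdose count of affected subjects is planned

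*SAP*

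**What the plan says.** **Where healthy subjects start.** On BPRS, SAP 9.1.1 states that "A score of 18 is generally expected for healthy volunteers". The same table gives 18 as the lowest possible total, on a range of 18 to 126. It adds that scores of 25 or more "reflect the presence of psychiatric symptoms and should be considered exclusionary". On CADSS, SAP 9.2.1 reports "Baseline scores for normal healthy males were 1.67 (2.96") on a scale of 0 to 92, and says of thresholds: "No official cut off criteria for scoring".

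**What is done after dosing.** BPRS and CADSS are taken at 6 and 24 hours on Days 1, 7 and 14, so six times per subject. SAP 9.6 fits a mixed-effects model to change and percent change in total score. The fixed effects are treatment, day and dose, with baseline as a covariate. The output is "P-values for key components of variance, least-square means (LSMeans), and 95% CI for contrasts will be output". Treatment-by-treatment descriptive statistics at each time point include quartiles, minimum and maximum, and there are graphs and listings.

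**Where the cut-off is used.** SAP 9.1.4 tabulates subjects with a BPRS total of 25 or more at Screening. Sections 9.1.4, 9.2.4, 9.4.4 and 9.6 plan no postdose count of subjects on BPRS, CADSS or 3MS. The Alertness VAS, by contrast, gets a per-subject maximum and minimum (SAP 9.5.2).

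**The risk.** Protocol Appendix 14 says that mGlu5 inhibitors, including TMP-301, "are associated with psychiatric adverse events which can include dissociation and hallucination".

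**The concern.** Psychiatric assessments are part of the primary safety endpoint, and dissociation and hallucination are things that happen to individuals. If unaffected subjects hardly move from the floor, a mean contrast with 6 subjects per active group spreads one person's reaction over the group, and that same reaction inflates the residual variance. The only inferential output could then read as no difference in a cohort where one subject in six reacted strongly. The SAP already states a score that it regards as symptomatic, but it does not count who reaches that score on treatment.

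**Working it through.** **Inputs.** Each cohort is 6 active and 2 placebo (SAP 3.1), with placebo pooled. Full enrolment gives 6/6/4 with 2 cohorts, 6/6/6/6 with 3 and 6/6/6/6/8 with 4, placebo last. No power, effect size or SD is stated for these contrasts, and the 24 subjects in SAP 3.5 have no formal basis, so there is no planned precision to reproduce. The scale limits do reproduce: BPRS 18 × 1 = 18 to 18 × 7 = 126; CADSS 23 × 4 = 92.

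**Step 1: the floor.** For BPRS the expected score is the scale minimum. For CADSS the SD (2.96) exceeds the mean (1.67). A normal curve with those values would put 29% of scores below zero. A gamma-Poisson fit puts 52% at exactly zero.

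**Step 2: one reactor.** One of 6 active subjects rises by x, and nobody else changes. One value per subject, variance pooled over all groups, N subjects, k groups, m placebo.
- Mean difference = x/6.
- Residual sum of squares = x² − 6(x/6)² = (5/6)x².
- SE = x·√[(5/6)/(N − k) · (1/6 + 1/m)].
- x cancels from t = (1/6) / √[(5/6)/(N − k) · (1/6 + 1/m)].

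| Cohorts | N − k | m | t | p | 95% CI if BPRS goes 18 to 40 (difference 22/6 = 3.7) |
|---|---|---|---|---|---|
| 2 | 13 | 4 | 1.02 | 0.33 | −4.1 to 11.4 |
| 3 | 20 | 6 | 1.41 | 0.17 | −1.7 to 9.1 |
| 4 | 27 | 8 | 1.76 | 0.09 | −0.6 to 7.9 |

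A rise to the scale maximum gives the same p-values. With two equal reactors among 6, p is 0.13 with 2 cohorts and 0.01 with 4, so the insensitivity is mainly to a single reactor.

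**Step 3: repeated measures.** The listed terms include no treatment-by-time interaction. If the treatment effect is averaged over six assessments, a 30-point rise in one subject at one assessment adds 30/(6 × 6) = 0.83 to the group mean.

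**Step 4: interval coverage (simulated, reaction rates and sizes assumed).** Assume reactors rise by a mean of 15 (SD 5), others change by −1, 0 or +1, with one value per subject and a pooled variance.
- *Only one active group reacts*, at rate 1/6, 1/3 or 1/2: nominal 95% intervals cover 65%, 86% and 90% with 2 cohorts, and 60%, 72% and 73% with 4. At 1/6 nearly all the misses understate the effect. The main reason is that no reactor appears in (5/6)⁶ = 33% of groups of 6.
- *All active groups react at those rates*: coverage is 88% to 98%.
- *No effect*, in a separate baseline-adjusted simulation: CADSS 95% to 96%, BPRS 97% to 99%.
- That same simulation, with all active groups reacting at 1/12 or 1/6, gave 95% to 97% for CADSS and 88% to 96% for BPRS with 4 cohorts. With 2 cohorts it gave 88% to 92% and 71% to 87%. The lowest value is BPRS at rate 1/12, where few reactors are seen at all.

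**Step 5: what a count shows.** One of 6 subjects at 25 or more is 16.7%, exact 95% CI 0.4% to 64.1%. For 0/n the upper limit is 1 − 0.025^(1/n): 45.9% for 0/6 and 36.9% for 0/8.

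**The case against.** The strongest reply is that the contrast is not how this trial would detect a reaction. A jump from 18 to 40 would be the maximum at that time point, would stand in the listings and graphs, and under Protocol Appendix 14 the scheduled scale responses are reviewed for psychiatric adverse events, which are then tabulated. This stands. A reader might infer that the plan would miss a severe reaction; the documents do not support that. What remains is that maxima by time point do not show how many distinct subjects were affected, or whether the same subject recurs.

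A reader might also infer that the confidence intervals are wrong in general. They are not: coverage is at or above nominal with no effect and mostly close to it when all active groups react. The low figures need few reactors, typically in one group. Appendix 14 describes a class risk, so effects in several dose groups are at least as plausible. The simulations also use one value per subject, not the SAP's repeated-measures model, so they indicate a direction and not that model's coverage.

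Giving each group its own residual variance looks like a natural repair, but it is not a safe one. At rate 1/6 its coverage is about 66%, whether one or all active groups react, and in the second case that is lower than with a pooled variance. With every placebo subject unchanged, the placebo variance is estimated as zero.

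Finally, not every threshold in the SAP is suitable for a postdose table. The values 31, 41 and 53 are introduced with "Total Score cutoff criteria for patients diagnosed with schizophrenia or experiencing psychosis are", CADSS has no cut-off, and the 3MS value of 77 concerns dementia. Only BPRS 25 is described in terms that fit healthy subjects.

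**Conclusion.** The point holds in a limited form. By the SAP's own figures BPRS and CADSS start at or near the floor. One reactor among 6, with no other change, cannot bring the contrast with placebo to p < 0.05 at any planned size (p = 0.33, 0.17, 0.09). That result is exact arithmetic for one value per subject with a pooled variance; noise in other subjects or the full model would alter the figures. Intervals that are too narrow are a possibility when few subjects react, resting on assumed reaction rates, and not a general property. The gap in reporting is certain from the text: the BPRS cut-off of 25 is counted at Screening and never after dosing. Because individual reactions remain visible elsewhere, this is a cheap improvement to the primary safety summary and not a failure of safety detection.

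**What to change.** Add to SAP 9.6 one table by treatment (each TMP-301 group and pooled placebo) built on each subject's worst postdose value:
- number and percent of subjects with any postdose BPRS total of 25 or more, with exact 95% CIs;
- distribution of worst CADSS increase from baseline;
- distribution of worst 3MS decrease from baseline.

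State in the same section that a non-significant LSMeans contrast is not evidence of no psychiatric effect. Keep the planned model, labelled exploratory. Do not add separate variances or the patient cut-offs of 31, 41 and 53.

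The cost is one table from data already collected. The counts cannot separate drug from placebo at these sizes, but their wide exact intervals make that plain to the reader.

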10 PHARMACOKINETIC ANALYSIS

The PK analysis will be carried out according to Altasciences SOPs.

10.1 Missing Values

The lack of concentration values due to failure to collect the sample, a lost or compromised sample or due to the subject's early termination from the study will be termed "missing" in the dataset, and no imputation will be done.

If the actual collection time of a postdose PK sample is unknown, but a valid concentration value has been measured, the sample will be set to missing in the PK analysis and will be presented in listing excluded from descriptive statistics.

10.2 Measurements Below the Lower Limit of Quantitation

Concentration values below the lower limit of quantitation (LLOQ) associated with predose and postdose collection times will be replaced with zero for the non-compartmental analysis (NCA).

Concentration values below the LLOQ will be replaced with zero for mean PK profile representations as well as for descriptive statistic calculations.

Concentration values below the LLOQ that are embedded between two quantifiable concentrations will be replaced with missing for mean PK profile representations as well as for descriptive statistic calculations.

10.3 Actual Time

The NCA will be based on actual sampling times.

The individual concentration-time profiles will be presented using actual sampling times whereas the mean concentration-time profiles and tables presenting summary statistics of concentration-time series will be presented using nominal sampling times.

10.4 Non-Compartmental Analysis

The following configuration for the NCA analysis (with Phoenix® WinNonlin® version 8.0, or higher) will be used:

• Data:	Serial sampled data
• Model/Dose options Type:	Plasma (200 -202) / Extravascular
• AUC Calculation Method:	Linear Up Log Down
• Lambda z (λ_z) calculation:	Best fit method for λ_z Linear-Log regression

Reasons for excluding PK parameters will include the following:

- AUC: AUC parameters will not be estimated if less than 3 consecutive measurable concentrations are observed
- PK parameters requiring λ_z estimation (eg, Vz/F) will be set to Not Reported (NR) in the tables and listings if they meet one of the following:
 - $R^2 < 0.8$

The PK parameters for TMP-301 are presented in Table 6.

Table 7: Pharmacokinetic Parameters of TMP-301

Parameter	Definition
PK Parameters Day 1	
C_{\max}	Maximum observed concentration occurring at time T_{\max} after the first dose
T_{\max}	Time of maximum observed concentration after the first dose
AUC_{0-12} , (For BID dosing)	Area under the concentration time curve over the dosing interval, calculated from 0 to 12 hours (dosing interval) after the first dose (The nominal time will be used to estimate AUC using the NCA built-in tool in Phoenix® WinNonlin®. This means that actual times off by more than 1 minute from tau will be extrapolated/intrapolated as per Phoenix® WinNonlin®'s built-in formulas. If extrapolation/intrapolation is not possible, then no value is reported by the software.)
AUC_{0-24} , (For QD dosing)	Area under the concentration time curve over the dosing interval, calculated from 0 to 24 hours (dosing interval) after the first dose (The nominal time will be used to estimate AUC using the NCA built-in tool in Phoenix® WinNonlin®. This means that actual times off by more than 1 minute from tau will be extrapolated/intrapolated as per Phoenix® WinNonlin®'s built-in formulas. If extrapolation/intrapolation is not possible, then no value is reported by the software.)
C_{12}	Observed concentration occurring at time 12 h
C_{24}	Observed concentration occurring at time 24 h (C_{24} Day 1 = C_{trough} Day 2)
PK Parameters Days 2, 5, 7, 9, 11 and 12	
C_{trough}	Observed concentration at the end of the dosing interval
PK Parameters Day 14	
$C_{\max, ss}$	Maximum observed concentration at steady -state occurring at time $T_{\max, ss}$
C_{avg}	Average concentration, calculated as $AUC_{0-\text{Tau}, ss}/\text{Tau}$
$T_{\max, ss}$	Time of maximum observed concentration at steady-state
$C_{\min, ss}$	Minimum observed concentration after the first dose of a multiple regimen
$AUC_{0-\text{TAU}, ss}$	Area under the concentration time curve over the dosing interval at steady-state. (The nominal time will be used to estimate AUC using the NCA built-in tool in Phoenix® WinNonlin®. This means that actual times off by more than 1 minute from tau will be extrapolated/intrapolated as per Phoenix® WinNonlin®'s built-in formulas. If extrapolation/intrapolation is not possible, then no value is reported by the software.) For QD dosing: $AUC_{0-\text{TAU}, ss} = AUC_{0-24, ss}$ For BID dosing $AUC_{0-\text{TAU}, ss} = AUC_{0-12, ss}$
$C_{12, ss}$	Observed concentration occurring at time 12 h

Parameter	Definition
$C_{24,ss}$	Observed concentration occurring at time 24 h
CL/F	Apparent total clearance at steady-state, calculated as Dose/ $AUC_{0-TAU,ss}$
V_z/F	Apparent volume of distribution at steady-state, calculated as Dose/ λ_z * $AUC_{0-TAU,ss}$
AR_C _{max}	Accumulation ratio derived as $C_{max,ss} / C_{max,FD\ Day\ 1}$
AR_AUC _{0-12 BID}	Accumulation ratio derived as $AUC_{0-12,ss} / AUC_{0-12,Day\ 1}$
AR_AUC _{0-24 QD}	Accumulation ratio derived as $AUC_{0-24,ss} / AUC_{0-24,Day\ 1}$
AR_C ₁₂	Accumulation ratio derived as $C_{12,ss}/C_{12,Day\ 1}$
AR_C ₂₄	Accumulation ratio derived as $C_{24,ss}/C_{24,Day\ 1}$ ($C_{24\ Day\ 1} = C_{trough\ Day\ 2}$)
CYP1A2_ratio	Ratio of CYP1A2 activity derived as paraxanthine/caffeine concentration day 14 / paraxanthine/caffeine concentration day -1
The following PK parameters will be used for PK calculation on Day 14 and presented in the PK listings only	
λ_z Upper	Upper limit on time for values included in the calculation of λ_z
λ_z Lower	Lower limit on time for values included in the calculation of λ_z
λ_z	Apparent elimination rate constant, estimated by linear regression of the terminal linear portion of the log concentration versus time curve
R ²	Goodness of fit for the terminal phase
Number of Points	Number of data points in computing λ_z

